5.1 If Yes, what procedures are in place to assure safety?

ID: VIEW4E09460F5EC00
Name: v2_Surveys/Questionnaires

View: v2_Data Collection / Record Review

Data Collection/Record Review

You indicated on the "Type of Research" page that your study involves data collection or record review (i.e., chart review, not self-report).

1 * What type of data will be collected/analyzed in this study? (Check all that apply)
Prospective (data is not yet in existence and/or collected)

2 * Will this study involve adding data to a registry or database for future use?
 Yes No

3 * Will the data be released to anyone not listed as an investigator on the protocol?
 Yes No

3.1 If Yes, give name(s) & affiliation(s):

ID: VIEW4E0E25A8CA400
Name: v2_Data Collection / Record Review

View: v2_Pro prospective Data

Prospective Data

You indicated that the study involves the collection of prospective data.

1 * Where is the data being collected from? (Check all that apply)
Medical records
Other

1.1 If Other, please specify:
Functional gait and balance assessments and other training data related to the proposed interventions.

2 * What data fields will you have access to/collect for the study? For example, name, initials, date of birth, Social Security number, income, demographic information, family units, housing, etc.
Name
Date of birth
Soc Sec (for VA forms only)

You can also upload a copy of the data fields/variables to be collected for the study:

Name	Created	Modified Date
There are no items to display		

ID: VIEW4E0E25B643800
Name: v2_Pro prospective Data

View: v2_Clinical Trial Registration

Clinical Trial Registration

You indicated on the "Type of Research" page that your study is a clinical trial.

1 * Does the UM Clinical Trials Registry policy require registration of this trial?
 Yes No

2 * Has this trial been registered?
 Yes No

ID: VIEW4E093BF078C00
Name: v2_Clinical Trial Registration

View: v2_Participant Selection

Participant Selection

1 * How many local potential participants (or specimens/charts) do you anticipate will be screened for this study? **Screening includes determining potential participants' initial eligibility for and/or interest in a study.**
150

- 2 * How many participants (or specimens, or charts) will be enrolled/used for this study? **A local prospective participant is considered enrolled in the study when a UM-approved Informed Consent Document (not including separate screening consent forms) is signed.**

Local - the number being enrolled at this site:

100

Worldwide - the number being enrolled total at all sites (including local enrollment):

100

- 3 * Gender:

Male

Female

- 4 * Age(s):

18 years and older (Adult)

- 5 * Race/Ethnicity:

All Races Included

- 6 * Language(s):

English

- 6.1 Specify Other:

- 7 * Are you excluding a specific population, sub-group, or class?

Yes No

- 7.1 If Yes, indicate your justification for excluding a specific population, sub-group, class, etc.:

ID: VIEW4E0E519C1D000
Name: v2_Participant Selection

View: v2_Vulnerable Populations

Vulnerable Populations

- 1 * Will you be including ANY of the following Vulnerable Populations? (Select all that apply)

None of the above

You may not include any members of the above populations as subjects in your research unless you indicate this here.

ID: VIEW4E0E519917800
Name: v2_Vulnerable Populations

View: v2_Eligibility

Eligibility

- 1 * Do you have an existing Eligibility checklist(s) for this study?

Yes No

- 1.1 If Yes, upload here. If you need a template, you can download it by clicking **HERE**. The checklists you upload will also be available under the Documents tab of this application.

Name	Created	Modified Date
------	---------	---------------

There are no items to display

- 1.2 If No, create an eligibility checklist below:

List inclusion criteria (List each Inclusion Criteria individually, using the ADD button):

Number	Criteria
View 1	In the chronic phase of stroke (> 6 mos. post-stroke) with residual hemiparesis of the lower extremity that includes symptoms of foot-drop.
View 2	Clear indications of hemiparetic gait by clinical observation.
View 3	Completed all conventional physical therapy.
View 4	Ability to walk on a treadmill with handrail support.

List exclusion criteria (List each Exclusion Criteria individually, using the ADD button):

Number	Criteria
View 1	Cardiac history of (a) unstable angina, (b) recent (less than 3 months) myocardial infarction, congestive heart failure (NYHA category II); (c) hemodynamically significant valvular dysfunction.
View 2	Major clinical depression: CESD score > 16 and judgment of clinical depression
View 3	Hypertension that is a contraindication for a bout of treadmill training (greater than 160/100 on two assessments).
View 4	Medical History: (a) recent hospitalization (less than 3 months) for severe medical disease, (b) symptomatic peripheral arterial occlusive disease, (c) orthopedic or chronic pain conditions that significantly alter gait function, (d) pulmonary or renal failure (e) active cancer
View 5	History of non-stroke neuromuscular disorder restricting gait.
View 6	Aphasia or cognitive functioning that confounds participation, defined as unable to follow 2 step commands. The Mini Mental State Exam will be administered with a cut-off of less than 23 (less than 17 if education level at or below

8th grade), or judgment of the medical officer.

After entering the inclusion and exclusion criteria above, click the Save link. CICERO will automatically generate a printable Eligibility Checklist for you to use in your research. To review the checklist, click on the resulting link below. This checklist is also available under the Documents tab of this application.

Eligibility Checklist for HP-00062671 v3-9-2015-1425909209986(0.01)

ID: VIEW4E0E5185F9000
Name: v2_Eligibility

View: v2_Recruitment

Recruitment

1 * Describe plans for recruitment, including the identification of potential participants (or acquisition of charts/records/samples) and initial interactions with them:

Some participants with stroke will be recruited by IRB approved flyers or word of mouth. Initial interactions will consist of a phone call from a research staff member stating that we are contacting the individual based on their expressed interest in the study. Other participants will be recruited from the University of Maryland Rehabilitation & Orthopaedic Institute Stroke Registry (UMROI) Stroke and Pepper Center registries which are approved by UMB IRB. Other participants will be recruited using specialized searches on VA CPRS. The UMROI Stroke Registry, Pepper Center Registry and VA CPRS will all be used to identify and conduct preliminary screening of potential participants. Initial interactions will consist of a phone call from a research staff member stating that we are contacting the individual based on their prior willingness to be contacted about new research studies and asking if they would be interested at this time in learning about our new project. If they are interested in learning more about the study, the caller will briefly outline the study and describe the initial visit that includes the Geriatric Assessment Clinic (GAC) for obtaining informed consent and assessment of eligibility for the study. If still interested the caller will inquire about available times that the potential participant could come to the Baltimore VAMC, and subsequently schedule an appointment for the initial visit. During this initial phone contact, research staff will not request the veteran's social security number.

During recruitment and screening, patients with major neurocognitive impairment, depression, dementia or elements of aphasia that would interfere with the study are identified and excluded. Those interested in the study and with no apparent exclusionary criterion at the time of initial screening are scheduled to come in to hear about the study in detail and carefully go over the consent with trained staff. Any of the co-investigators or staff listed on the protocol, may obtain consent prior to the GAC assessment.

We will attempt to enroll as many Veteran participants as possible in this VA-funded human research study. However, we do anticipate recruitment of at least some non-veterans, assuming that recruitment of Veterans-only may prevent timely completion of this 4-year randomized controlled study. Also, we may need to recruit non-veterans to expand the range of deficit severity in the stroke group, to better define future applicability of lower extremity robotics to studies in the larger stroke population. Scientifically we expect that results obtained from any non-veteran stroke survivors will be similar to that potentially gained from veterans who have had a stroke, and data from qualified healthy volunteers should also be similar to that of healthy Veterans.

We will also use IRB-approved flyers to be posted in the surrounding community. Respondents will call the listed phone number and the above process will be carried out as with those re-contacted via the registry.

2 * Describe measures that will be implemented to avoid participant coercion or undue influence (if not applicable to the study, enter "N/A"):

Participants will be informed that they have an absolute right to withdraw from the study at any time for any reason. It will be emphasized upon withdrawal that they will not lose eligibility for medical care or services at the VA or University of Maryland Medical Center, nor will they lose eligibility to participate in any future research studies. Informed consent will follow institutionally approved guidelines, including protection of confidential information relating to medical history and other information gathered to determine eligibility criteria.

3 * Who will recruit participants (or acquire charts/records/samples) for this study? (Check all that apply)
Study Staff

3.1 If you are using a third party, specify Third Party Recruiters:

4 Upload any recruitment tools such as screening/telephone scripts and introductory letters (do not upload advertisements here):

Name	Created	Modified Date
There are no items to display		

ID: VIEW4E0BCAA0A6C00
Name: v2_Recruitment

View: v2_Advertising

Advertising

1 * Will you be using advertisements to recruit potential participants?

Yes No

ID: VIEW4E0BCCF811000
Name: v2_Advertising

View: v2_Advertising Detail

Advertising Detail

You indicated that you will be using advertisements to recruit potential participants.

1.1 * Select the mode(s) of advertising (check all that apply):

Other

1.1.1 If Other, specify:

Flyers

1.2 * Provide exact text of all proposed advertisement(s):

Stroke Survivors Needed for Robotics Research.

18-90 year-old volunteers who are at least 6 months post-stroke are needed for a research

study investigating use of an ankle robot in gait and balance rehabilitation after stroke.

If you would like to learn more or would like to participate, please call [contact].

Baltimore Veterans Affairs Maryland Health Care System,
[name].

1.3 * Upload advertisement(s) here:

Name	Created	Modified Date
Stroke Survivors Needed for Robotics Research.docx	3/11/2015 12:18 PM	3/11/2015 12:18 PM

ID: VIEW4E0BC8288C00
Name: v2_Advertising Detail

View: v2_Research Related Risks

Research Related Risks

If you uploaded a separate research protocol document in the 'Research Protocol' page, cite the applicable section and page numbers from that document in the answer box below.

- * Individually list each research-related risk, using a separate line for each. Next to each risk, delineate the likelihood/seriousness of the risk, and the provisions for minimizing the risk:
 - There is a risk that repeated movements while wearing the ankle robot may cause skin irritation at contact points. This risk is greatly reduced by using extra foam padding to securely fit the robot. Also, regular inspection of the attachments and queries to the subject are used to prevent this problem from developing.
 - During overground and treadmill walking tests or training there is a minimal risk of falling. The likelihood of falling is reduced by the use of a gait belt and/or safety harness with close supervision by study personnel.
 - There is a small risk that you will fall, get chest pain, shortness of breath or become dizzy. There is a small risk of muscle strain or pulled muscles in the measurement of strength. The test will be stopped if you have any symptoms such as chest pain. We have performed more than 1000 tests of functional performance without complication.
 - There is a very slight risk that the robot could move the foot in the wrong direction causing injury. This is extremely unlikely as maximal torque outputs by the robot are not sufficient to induce muscle, tendon, or ligament injuries. Further protection is provided by failsafe switches that turn the robot off in 2 ms.
 - Treadmill exercise testing risks are minimal, but occasionally include fainting, dizziness, chest pain, or irregular heartbeats. A heart attack may occur, but this is extremely rare (< 1 death in 10,000 tests) in people without a history of heart disease. To reduce these risks, blood pressure, heart rate and rhythm, and breathing are continuously monitored during exercise testing by an MD and personnel trained in CPR, exercise testing, and emergency treatment. Emergency medications and resuscitation equipment are available.
 - There is a risk of muscle soreness after exercise tests and training. This is a relatively rare occurrence for submaximal efforts, but it is more likely in the early stages of training when subjects are unused to the exercise activities. The risk is reduced by providing regular opportunities to rest.
 - There is a small risk that subject privacy/confidentiality may be compromised. Several procedures are in place to minimize this risk. Participants are provided privacy during research interactions with the research team. The PI and research team will keep identifiers linking names to research codes in a secure file locked in a cabinet in the locked research space or the PI's office. Only the PI and research team will have access to this information on an as-needed basis. Only the research codes will be used for data collection and training records.
 - Screening and treadmill testing will be done at the Baltimore VA Medical Center, where a crash cart and emergency medications are available.
 - For medical emergencies that occur at the Baltimore VA Medical Center Annex or the Baltimore VA Loch Raven facility, an AED is available on site and the 911 emergency medical system would be activated by the research team.

ID: VIEW4E1B52509F000
Name: v2_Research Related Risks

View: v2_Potential Benefits and Alternatives

Potential Benefits and Alternatives

If you uploaded a separate research protocol document in the 'Research Protocol' page, cite the applicable section and page numbers from that document in the answer boxes below.

- * Describe the potential direct benefit(s) to participants:
The participant may or may not benefit by taking part in this study. There is no guarantee that the participant will receive direct benefit from participating in this. A potential benefit of participation is to help in the development of new robotic therapies for stroke survivors. There is a potential benefit in defining those who can successfully use this new robotic approach after stroke.
- * Describe the importance of the knowledge expected to result from the study:
As our adult population ages, the number of strokes in the United States is anticipated to double, reaching nearly 1.5 million annually by the year 2050. The opportunity to define the appropriate use of rehabilitation robotics in the restoration of gait and balance functions in this population has major implications for improving overall mobility and reducing risks for further debilitating injuries through falls. In addition, the use of robotics affords a unique opportunity to study the processes of motor learning that inform contemporary rehabilitation strategies and suggest optimal approaches for mediating mechanisms of neuroplasticity. These benefits outweigh the minimal risks that may arise from using robotics in a controlled rehabilitation setting.
- * Describe how the potential risks to participants are reasonable in relationship to the potential benefits:
By comparing the effects of robotics treadmill training to treadmill only training we will advance our understanding of how these specific approaches may impact the crucial functional areas of locomotion and balance control. This work is essential to provide the evidence base needed to objectively define appropriate use of lower extremity robotics in the rapidly evolving field of stroke rehabilitation. The risks of using the ankle robot in closely supervised training conditions are minimal, compared to the potential positive impact on participants and on the longer term goal to develop effective robotic therapies that could enhance the health and quality of life of millions of other stroke survivors.
- * Describe the alternatives to participation in this study. If there are no alternatives, state that participation is voluntary and the alternative is not to participate. For intervention studies, describe appropriate alternative clinical procedures or courses of treatment available to subjects.
There are no alternatives to participation in this study. Participation is voluntary and the alternative is not to participate.

ID: VIEW4E1B5251B0400
Name: v2_Potential Benefits and Alternatives

View: v2_Withdrawal of Participants

Withdrawal of Participants

If the questions below are not applicable to the research (i.e., chart review), enter "N/A".

- 1 * Describe anticipated circumstances under which subjects will be withdrawn from the research without their agreement:
Participants may be withdrawn from the research without their prior agreement under the following circumstances:
- poor attendance leading to insufficient training
- entering participation in other exercise protocols or activities that would confound results of this study
- emergent medical problems that preclude continuing with the training protocols
- 2 * Describe procedures for orderly termination:
Orderly termination of the study will occur at the conclusion of the final measurement session. At that time the participant will be informed of any interim results to indicate how they have performed during the course of the study if they request such information. In the event that a participant requests an early termination, the study PI or research staff will discuss the reasons and offer any interim feedback available on the participant's progress during the study at that point.
- 3 * Describe procedures that will be followed when subjects withdraw from the research, including partial withdrawal from procedures with continued data collection:
When participants withdraw a note will be placed in their file indicating their reasons for withdrawal.
In rare cases if a participant is unable to complete all planned procedures but it is determined that this will not compromise the scientific integrity of the study a note will be made to file explaining the circumstances.

ID: VIEW4E1B52531F800
Name: v2_Withdrawal of Participants

View: v2_Privacy of Participants

Privacy of Participants

If the study does not involve interaction with participants, answer "N/A" to the questions below.

- 1 * Describe how you will ensure the privacy of potential participants throughout the study (**privacy refers to persons and their interest in controlling access to themselves**):
Privacy will be ensured during the consenting process by having the potential participant meet with study personnel in a private office, or in the VA Human Motor Performance Laboratory or other private setting to review consent forms and discuss study procedures. Only trained staff will conduct these meetings and the participant's identity will never extend beyond the research team.
- 2 * Describe the location where potential participants will receive research information and detail the specific actions the study team will take to ensure adequate privacy areas:
Screening and consent activities with participants will be conducted in the Baltimore VAMC Geriatric Assessment Clinic or VA Human Motor Performance Laboratory and/or Loch Raven Robotics and Exercise Center in a private examination/interview area, or in another private office area, away from public traffic where only the member(s) of study research team may see or overhear the participant.
- 3 * Describe potential environmental stressors that may be associated with the research:
This research will not introduce new environmental stressors to the participants.

ID: VIEW4E1B525B87C00
Name: v2_Privacy of Participants

View: v2_Confidentiality of Data

Confidentiality of Data

- 1 * Will stored research data contain identifiers or be able to be linked to and identify individual participants (either directly or through a code/research ID)?
Yes
- 2 * Where will research data be kept (address electronic and paper data as applicable)?
All research subjects are assigned a unique identifying number and all data processing is done utilizing this number rather than name, social security number, birth date or other specific individual identifying information. All research data with identifiers are kept in locked cabinets, and all digital data on research computers are protected by network firewalls and passwords. The data collected will be used for research purposes only. Analysis will primarily be in the form of averaged group results. Electronic data will be stored on VA servers while paper is stored in a locked room.
- 3 * How will such data be secured?
A master file with the names and numbers of the research subjects will be maintained by the PI and kept in a locked file cabinet in a locked area. All data from tests and training will be de-identified and recorded into electronic file formats that will be stored behind the firewall and password protected network. Transmission of any electronic data will utilize file encryption. No data will be stored on a hard drive. All data will be stored on a server and backed up daily on server
V:\whabalrsch1\hmpl_share\Footdrop Merit
As per current VA policy, all data, including the investigator's research records and any participant identifiers will be retained in accordance with the Dept. of Veterans Affairs Records Control Schedule (RCS 10-1), and will not be destroyed. If at a later date the VA policy changes data will be destroyed using the most current approved methods available.
- 4 * Who will have access to research data?
Only the PI and his research team will have access to the research data.
- 5 * Will study data or test results be recorded in the participant's medical records?
 Yes No
- 6 * Will any data be destroyed? (**Please note that data for FDA regulated research and VA research cannot be deleted**)
 Yes No
- 6.1 If Yes, what data (e.g., all data, some recordings, interview notes), when and how?
- 7 * Do you plan to obtain a Certificate of Confidentiality?
 Yes No

- 7.1 If Yes, upload your Certificate of Confidentiality. If you have not yet obtained the Certificate, please note that once it is obtained, you will need to submit an amendment to attach the document, make any needed changes to the submission and make needed changes to the Informed Consent Document.

Name	Created	Modified Date
There are no items to display		

- 8 * Discuss any other potential confidentiality issues related to this study:
No research data will be removed from the VA protected environment. All access to data will be terminated when a staff member leaves employment or is no longer a member of the research team. If there is a loss of data, unauthorized access to sensitive data, or non-compliance with security controls it will be immediately reported to the PI, and the appropriate VAMHCS Privacy Office and Information Security Personnel. The VA Research Compliance Office and IRB will also be notified.

ID: VIEW4E1B526E0400
Name: v2_Confidentiality of Data

View: v2_Monitoring Plan Selection

Monitoring Plan Selection

- 1 * Type of data safety monitoring plan for the study:

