3.1 If Yes, when?

4 * Briefly describe the DSM review process itself. Will it be an open or closed review to the investigator? Blinded/unblinded data? How will confidentiality of individual participant data be maintained?

Committee meets bi-annually to review all adverse events, enrollment status, audit results or study related procedures. The committee may also meet on an ad-hoc basis if needed. Attendance is open to investigators but PI's must recuse themselves from actual decision making of their own study. Participants are de-identified for purposes of committee discussion and determination of action plans

FROM BMI

The DSM process involves updating on any adverse events and how they have been addressed. Also the basic progress of the study will be reported generally (enrollments etc.). If deemed necessary the board will make recommendations on whether additional modifications in the protocol are warranted. This can be an open review to investigators or study coordinators. Discussion of cases involving specific participants will not refer by their name(s) but by coded identifiers. Other PHI may be needed to fully characterize such cases, but these will not be reported beyond what is minimally necessary to provide the DSMB sufficient information to arrive at a decision

5 * What are the criteria defined in the protocol to be used for decision making regarding continuation, modification, or termination of study?

If the participants are tolerating the treadmill and ankle robot sessions without any adverse reactions, the study will be continued. If the participants are having difficulty staying engaged with the walking or robot games for the full session, leading to incomplete exposure to the exercise and robotics modalities, then they will be withdrawn from the study. If a participant develops a condition, such as ankle sprain or acute gout, which would preclude participation in the study, or if there is an emergent inability to perform either form of exercise, the participant will withdraw from the study. A participant who becomes medically unstable may temporarily suspend participation in the study, but re-enter when the condition is resolved

FROM BMI

The criteria are based first on the safety of participants and second on their compliance with protocol as they move through the study phases.

The UM IRB and VA R&D will make all decisions regarding continuation, modification, or termination of the study.

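### Withdrawal from the research for poor attendance can remove primary outcomes from the intention-to-treat analysis, and the SAP plans no analysis of how far β4 depends on missing at random

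*Protocol*

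**What the plan says.** **Protocol, Withdrawal of Participants, item 1.** The lead-in reads "Participants may be withdrawn from the research without their prior agreement under the following circumstances". The reasons listed include "poor attendance leading to insufficient training" and "emergent medical problems that preclude continuing with the training protocols". No number of sessions defines poor attendance.

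**Protocol, internal DSMB monitoring plan, item 5.** Patients who are "having difficulty staying engaged with the walking or robot games for the full session" are covered by a firmer rule: "leading to incomplete exposure to the exercise and robotics modalities, then they will be withdrawn from the study". For medical reasons the text reads "emergent inability to perform either form of exercise, the participant will withdraw from the study", although a medically unstable patient may suspend and later re-enter.

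**Protocol, Withdrawal of Participants, item 3.** The form asks what happens on withdrawal, including partial withdrawal with data collection continuing. The answer is "When participants withdraw a note will be placed in their file indicating their reasons for withdrawal", followed by an exception that begins "In rare cases if a participant is unable to complete all planned procedures" and also ends in a note to file. Neither sentence mentions outcome testing.

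**Testing schedule.** Study Procedures item 1 and SAP 1.0 schedule testing at the end of training for patients in general. Neither says whether withdrawn patients are included.

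**SAP.** Section 2.2 makes intention to treat primary, whether or not the intervention was received, and concedes that missing outcomes breach it. Section 2.3 bases the primary analysis on β4, the group difference at the first follow-up, from a REML repeated-measures model. Section 2.5 assumes missing at random, gives non-return of the worst patients as an example of failure, and says the treatment effect is biased only if the departure differs by arm. Section 3.2 repeats the analyses in patients with at least 15 sessions.

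**The concern.** Intention to treat needs outcomes on patients who did not take the training as planned. The withdrawal rules act on those same patients and remove them from the research. Attendance and engagement can plausibly be related to outcome and to the arm, since only one arm wears the robot.

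A patient withdrawn during training has a baseline value and nothing later. The illustration in SAP 2.5 is a patient who misses the second follow-up but is seen at others, whose gap is filled from later and earlier values. A patient with baseline only is predicted from baseline, covariates and the measured patients of the same arm. If withdrawn patients do worse (or better) than that prediction, β4 departs from the intention-to-treat effect.

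The one alternative analysis sample, in SAP 3.2, leaves out patients with fewer than 15 sessions, so it cannot show what their missing outcomes would do. The protocol's compliance analyses serve a different purpose.

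**Working it through.** **Plan's own figure.** From Sample Size and Data Analysis item 1: 36 completers per group, 0.72 SD of change, two-sided 0.05 t-test. The noncentral t distribution gives 85.4% power, against 85% stated. At the 0.007 level and 0.90 SD it gives 84.7%. Both reproduce, and this point does not depend on any fault in them.

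**Room for loss.** 100 are to be enrolled, counted at consent, and 2 × 36 = 72 complete, so 28 may be lost after consent. That count includes screen failures. With S screen failures, loss after randomisation is (28 − S)/(100 − S):
- S = 15: 13/85 = 15.3%
- S = 20: 8/80 = 10%
- S = 25: 3/75 = 4%

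S is an assumption. The documents give no dropout rate, overall or by arm.

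**Bias formula.** Take higher as better. Let π be the fraction missing in an arm and δ the number of SDs of change by which missing patients fall below the model's prediction. Then

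bias in β4 = π_TMR × δ_TMR − π_TM × δ_TM.

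**Equal δ in both arms, unequal fractions** (δ = 0.3 / 0.5 / 0.8):
- 13% v 7%: 0.06 × δ = 0.018 / 0.030 / 0.048 SD
- 15% v 5%: 0.10 × δ = 0.030 / 0.050 / 0.080 SD

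As a share of 0.72 this is 2.5% (0.018/0.72) to 11.1% (0.080/0.72). Swapping the arms reverses the sign. So an equal per-patient departure does not protect the contrast.

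**Equal fractions, unequal δ.** At 10% missing per arm, δ differing by 0.3 to 0.8 SD gives 0.10 × 0.3 = 0.03 to 0.10 × 0.8 = 0.08 SD.

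**Type I error.** SE = √(2/36) = 0.236. With no true effect, the two-sided rejection rate (normal approximation) is 5.5% at a bias of 0.048 and 6.3% at 0.080. With baseline adjustment, SE = 0.236 × √((1 + ρ)/2). For an assumed ρ of 0.3 to 0.8 this is 0.190 to 0.224, and the rates are 5.5 to 5.7% and 6.5 to 7.0%.

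**Simulation check.** 40 per arm, withdrawn patients with baseline only, common baseline mean, 60,000 runs, δ = 0.8, ρ = 0.3 to 0.8. Losing 6 v 2 gave a bias of about 0.08 SD, and 2 v 6 about −0.08 SD. Type I error was about 6.4 to 7.0% in both. Losing 4 v 4 gave essentially no bias and about 5%.

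**Tipping point.** At the 0.05 level the smallest significant difference is t(0.975, 70 df) × 0.236 = 0.470 SD. With 10% missing per arm, significance is lost when the δs differ by:
- estimate 0.50: (0.50 − 0.470)/0.10 = 0.3 SD
- estimate 0.72: (0.72 − 0.470)/0.10 = 2.5 SD

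At 15.3% missing these become 0.2 and 1.6 SD. At the protocol's conditional 0.007 level the threshold is 0.655 SD, and an estimate of 0.72 tips at (0.72 − 0.655)/0.10 = 0.65 SD.

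**The case against.** **Some poor attenders are probably measured.** The general schedules are not limited to completers, the protocol's exception keeps some incomplete patients in, and SAP 3.2 speaks of removing non-attenders, which presupposes that some have data. This stands: the loss may be partial. It is still not a commitment to test withdrawn patients. A reader might infer that every poor attender is lost; the documents do not support that.

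**A commitment may exist elsewhere.** The consent form and some pages of the application are not in the text reviewed. The gap is therefore established only for the text available, though the item that asks the question directly is there and does not answer it.

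**SAP 2.5 already discloses the dependence.** A reader might infer that the plan hides its reliance on missing at random. It does not: 2.5 states the assumption and names the threat. What is absent is any measure of how sensitive β4 is to it.

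**May against will.** A reader might see a flat contradiction between the two protocol sections. The attendance and engagement triggers differ, and the medical rules, though close, sit beside a re-entry provision. This is mostly wording to reconcile.

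**The sentence in 2.5 can be read correctly.** It holds if the degree of departure includes how many patients are affected. It fails only on the per-patient reading, so it needs clarification rather than retraction.

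**The numbers are small and assumed.** True: 0.018 to 0.080 SD is 0.08 to 0.34 of one standard error, and the 0.50 SD example lies only 0.03 above the threshold. Nor can 28% be used as a dropout rate, because it includes screen failures.

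**Conclusion.** The concern holds in a limited form. Stated withdrawal rules work against the stated intention-to-treat aim, and the SAP names the resulting threat without planning to examine it. The plan should be changed on this point, but nothing here shows that the primary result is biased or that the trial is invalid.

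Neither size nor direction can be derived from the documents. The range of about 0.02 to 0.08 SD rests on assumed loss of 5 to 15% per arm and assumed departures of 0.3 to 0.8 SD. At the 0.05 level this could decide a result close to the significance threshold and would not overturn one near 0.72 SD. That robustness is weaker if the 0.007 level is applied. Confidence is medium, because how many withdrawn patients go unmeasured is unknown.

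**What to change.** **1. SAP (can be applied in full).** Report withdrawals and missing post-training outcomes by arm, reason and sessions attended. Add a delta-adjusted (tipping-point) analysis of β4, with δ varied separately in each arm. Clarify in 2.5 that an equal per-patient departure still biases β4 when the missing fractions differ by arm. The cost is some wording and one extra analysis.

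**2. Protocol, Withdrawal of Participants items 1 and 3, and monitoring plan item 5.** Reconcile the wording and separate stopping training from leaving the study, leaving the reasons for stopping training unchanged. Any randomised patient who has not yet passed the post-training assessment would still be invited to it, unless consent is withdrawn or testing is unsafe.

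The assessment takes two to three visits at $10 each, or $20 to $30 per patient, plus staff time and motion-analysis and force-plate testing. For 8 patients (10% of 80, assumed) that is 16 to 24 visits and $160 to $240 in vouchers.

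The intention-to-treat estimate may be somewhat diluted. The protocol change may also reach few patients, because the 2019 SAP describes randomisation in the past tense and notes a measure not collected in the last 10 to 15 patients. The SAP changes are useful regardless, and most of all if outcomes have already been lost.
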